5.1.6 Recorded Content

All therapy sessions will be recorded for research and training purposes. Audio/video recording means may include Digital A/V recording devices and Zoom local recording for in-person and remote visits, respectively. The recordings are necessary for developing the experimental treatment and assessing adherence to the Treatment Manual. Any requests for use of video outside of research and training requests will result in participants (or their health care proxy if the participant is no longer able to consent) receiving information on the request. They will have control over any presentation of this material beyond viewing by researchers or regulatory agencies.

The sponsor-investigator uses encrypted, secure technology to transfer and store recordings (e.g. DFCI's secured DropBox), but there is always a risk of a security breach. The sponsor-investigator is committed to taking preventative measures to avoid such an event. Only investigators/delegated study members will have access to this data. Recorded content will be erased from the recording device's memory disk once transferred. No recording will be stored on the cloud. In the case of a security breach, the participant and/or their families will be notified,

and all efforts will be made to minimize the dissemination of recorded content. Recorded contents will be destroyed by the Sponsor-Investigator after sufficient storage.

5.2. Pre-Treatment Criteria

5.2.1. Cycle 1, Day 1

- Vital signs in the normal range
- Palliative Prognosis Score ≥ 50 %
- No significant suicide risk
- No delirium
- No contra-indicated medication

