3. PARTICIPANT SELECTION

3.1 Eligibility Criteria

Version Date: April 18, 2023

- 3.1.1 Patients enrolled in hospice care at home
- 3.1.2 Age \geq 21 years.
- 3.1.3 Any terminal illness with respect of exclusion criteria
- 3.1.4 Palliative Performance Scale (PPS) \geq 40 % (see Appendix A)
- 3.1.5 Moderate-to-severe demoralization as measured by Demoralization Scale-II \geq 8 (see Appendix A)
- 3.1.6 Significant other or other caregiver present at home the night of study drug administration
- 3.1.7 No driving for 24 hours following study drug administration.
- 3.1.8 English proficiency
- 3.1.9 Ability to understand and the willingness to sign a written informed consent document.
- 3.1.10 Psilocybin is very likely to have no genotoxic effects. One study that directly focused on the mutagenic potential of psilocybin did not found this type of toxicity. 42 However, due to the lack of clinical and non-clinical studies on the effects of psilocybin on the developing human fetus, women and men of child-bearing potential and who are sexually active must agree to use an acceptable contraceptive method (hormonal or barrier method of birth control; abstinence) throughout their participation in the study. Should a woman become pregnant or suspect she is pregnant while she or her partner is participating in this study, she should inform her treating physician immediately. Men treated or enrolled on this protocol must also agree to use adequate contraception prior to the study, for the duration of study participation, and 4 months after completion of psilocybin administration.
- 3.1.11 Patients with first-degree relatives with schizophrenia or bipolar disorder may be eligible depending on their age and personal and family psychiatric history. The decision will be made by the principal investigator and study psychiatrist based on risk assessment.

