5.1.2 Treatment regimen

Version Date: April 18, 2023

Visit V1: baseline assessment + preparation session #1 (patient's home or remote)

V1 includes baseline assessment and a first preparation session with the study therapists (see section below for details about the therapy dyads).

Baseline assessment consists in patient-reported questionnaires that patients will complete on paper either on their own prior to V1 or with the help of a study staff member. Baseline assessment includes the following measurements (see details in section 5.1.5): the Functional Assessment of Chronic Illness therapy – Palliative Care (FACIT-Pal); the PROMIS pain interference scale (if pain presented); the Hospital Anxiety and Depression Scale (HADS A and D); the PROMIS social isolation scale; the Life Attitude Profile – revised, Death acceptance subscale (LAP-R, DA); the FACIT-spirituality; the Schedule of Attitudes Toward Hastened Death (SAHD). Consenting caregivers will complete the CarGOQoL and HADS at V1. In addition, the study psychiatrist will complete the C-SSRS and the CAM.

Following baseline assessments, the lead therapist (LT) and the co-therapist (CT) will conduct the first preparation session. The main objectives of the preparation sessions are to educate

patients and families on psilocybin-assisted therapy, to build rapport between them and the study therapists, and to identify intentions for the psilocybin session as well as personal themes and struggles that might impact the psilocybin experience.

V1 and V2 will be conducted within about a week to a month prior to the psilocybin session.

The duration of V1 will be up to 90 min (30 min assessment + 60 min preparation).

Visit V2: preparatory session #2 (patient's home or remote)

The second preparatory session (V2) will take place at home or remotely. Patients and therapists will conduct V2 assessments as indicated on the schedule of assessment (see 5.1.6) and continue to set expectations for treatment, discuss set and setting and build the therapeutic alliance.

The duration of V2 will be up to 75 min (15 min assessment + 60 min preparation).

Visit V3: psilocybin session (hospice facility) – day 0

The psilocybin session will take place in an individual room at the Care Dimensions Hospice House and will last 8 h (30 min assessment + 7h30 hour psychotherapeutic support).

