Abbreviations. LT: Lead Therapist; CT: Co-Therapist; PA. Research Assistant; DS-H: Demoralization Scale-II; HADS A and D: Hospital Anxiety and Depression Scale Anxiety and Depression; FACIT-Pal 14: Functional Assessment of Chronic Illness Therapy Palliative Care 14; PIS: Pain Interference Scale; LAP-R: Life Attitude Profile – revised, Death acceptance subscale; SIS: Social Isolation Scale; FACIT-Sp 12: Functional Assessment of Chronic Illness Therapy-Spiritual Well-Being 12; MEQ-30: Mystical Experience Questionnaire; CSQ: Challenging Experience Questionnaire; SAMD: Schedule of Attitude toward Hastened Death; C-SSRS: Columbia-Suicide Severity Rating Scale; CAM: Confusion Assessment Method; PPS: Palliative Performance Scale; RRPQ-R: Reactions to Research Participation Questionnaire Revised; CarGOQoL: CareGiver Oncology Quality of Life questionnaire.

(1) The "Last month" version will be administered at Screening (V1) and the "Since Last Visit" version will be administered at all other visits.

⁽a) Lares lever only
(d) These assessments will also be completed by the participant's cargiver at V1, V5 and V6a,...f
(e) Only if the patient indicates pain at a given assessment period.
(f) Only at V6a
(g) We anticipate that given their terminal condition, participants might not be able to complete these questionnaires or may only be able to complete part of them. To reduce administrative burden, we will not report those missing questionnaires as protocol violations.

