13. STATISTICAL CONSIDERATIONS

13.1. Primary outcome variables

This study is an open label, single center, concurrent mixed-methods phase 2 trial. The primary objective is to pilot test a novel protocol of psilocybin-assisted therapy in patients receiving hospice care. Primary outcomes will relate to the following features of feasibility:

[figure not shown]
• **Enrollment:** number screened per month; number enrolled per month; average time delay from screening to enrollment

- **Retention:** number of sessions completed; retention rates for study measures; reasons for dropouts
- Completion of assessment: proportion of planned assessments that are completed; duration of assessment visits; reasons for dropouts
- Acceptability: acceptability ratings; qualitative assessments; reasons for dropouts

Benchmark for feasibility: treatment and week 1 assessments will be successfully completed in at least 60% of recruited subjects.

Benchmark for acceptability: $\geq 80\%$ of subjects who completed Week 1 assessment will evaluate favorably (agree or strongly agree) acceptability on the global evaluation factors of the RRPQ (See section 5.1)

To guide our evaluation of acceptability in the proposed project, we will use seven component constructs as defined in the following figure: affective attitude, burden, ethicality, intervention coherence, opportunity costs, perceived effectiveness and self-efficacy.⁷²

Theoretical framework of acceptability (from Sekhon et al., 2017)

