13.3. Sample size and statistical plan

13.3.1. Sample size justification

Patients with a PPS score of 50% and above have a median survival of 43 days or greater.⁷³ We anticipate that we will need to treat at least 10 patients for feasibility data to be relevant. To account for patients who are unable to complete the intervention because of clinical decline, we plan to recruit 15 patients.

Assuming that treatment and week 1 assessment will be completed on 10-15 patients, the 90% exact binomial confidence intervals for the feasibility rate will be between (30.3%-85.0%) – for 10 patients - and (36.0%-81.0%) – for 15 patients.

Assuming that between 6 (out of 10) and 9 (out of 15) patients will be able to assess the acceptability, the 90% exact binomial confidence intervals for the acceptability rate will be between (41.8% - 99.1%) – for 10 treated patients, out of which 60% deem the procedure "feasible" - and (57.1% - 99.4%) – for 15 treated patients, out of which 60% deem the procedure "feasible".

We will use the treatment effect size calculated for this study to inform the sample size of the upcoming corresponding confirmatory trial.

Accrual targets are as follow:

Accrual Targets								
Ethnic Category	Sex/Gender							
Etimic Category	Females		Males		Total			
Hispanic or Latino	2	+	1	=	3			
Not Hispanic or Latino	6	+	6	=	12			
Ethnic Category: Total of all subjects	8 (A1)	+	7 (B1)	=	15 (C1)			
Racial Category								
American Indian or Alaskan Native	0	+	0	=	0			
Asian	1	+	1	=	2			
Black or African American	2	+	1	=	2			
Native Hawaiian or other Pacific Islander	0	+	0	=	0			
White	5	+	5	=	10			

Racial Category: Total of all subjects	8 (A2)	+ 7 (B2)	= 15 (C2)
	(A1 = A2)	(B1 = B2)	(C1 = C2)

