13.3.2. Safety analysis

The Safety Population will consist of all enrolled participants who receive study treatment. This population will be used for all summaries of participant accountability, demographic and baseline data, and safety information, including AE incidence.

The Full Analysis Set (FAS) will consist of all participants who receive the dose of psilocybin and will be used for all summaries of efficacy.

The Per Protocol (PP) population will consist of all participants in the FAS who do not have a major protocol deviation which is defined as a deviation which may significantly affect efficacy for that participant. Major protocol deviations will be reviewed and determined prior to database lock.

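### Entry is set at PPS 40% or more, but treatment requires 50% or more on an undefined score; if that score is the PPS, a patient who stays at 40% can be prepared and tapered but not dosed

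*Combined protocol and SAP*

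**What the plan says.** Entry criterion 3.1.4 is "Palliative Performance Scale (PPS) \geq 40" (per cent). The scale is printed in Appendix A3. The study calendar (section 11) defines the abbreviation as "PPS: Palliative Performance Scale" and schedules the PPS at every visit, including screening (V0) and the dosing visit (V3).

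The pre-treatment criteria in 5.2.1, headed Cycle 1, Day 1, list "Palliative Prognosis Score ≥ 50" (per cent). That name appears nowhere else in the text: not among the calendar's abbreviations or rows, and not in Appendix A.

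Three parts of the statistical section bear on the consequence. The feasibility benchmark in 13.1 is that "treatment and week 1 assessments will be successfully completed in at least 60% of recruited subjects". Section 13.3.1 explains the target number: "To account for patients who are unable to complete the intervention because of clinical decline, we plan to recruit 15 patients". It also cites survival: "Patients with a PPS score of 50% and above have a median survival of 43 days or greater".

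**The concern.** If the two scores are the same scale, entry and treatment use different cut-offs on it. A patient at 40% satisfies 3.1.4, is enrolled at V0, and may then spend time in preparation and come off an antidepressant. Unless the score rises by V3, 5.2.1 then withholds the dose. Unlike delirium or later deterioration, this barrier can be seen at screening. No stated PPS rule halts preparation or taper in between.

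Two things are at stake. The first is avoidable burden on hospice patients with moderate-to-severe demoralization. The second is the primary feasibility measure: such a patient may count as a non-completer for a reason other than decline after entry, which is the loss the 15-patient target is meant to absorb.

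**Working it through.** **Is the 5.2.1 score the PPS?** Probably. The PPS is the only percentage-scaled palliative score in the protocol, it is scheduled at V3, and 13.3.1 itself uses PPS 50%. If another instrument were meant, the criterion could not be applied, because that instrument is neither provided nor scheduled. The text needs correction either way.

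**Does the criterion apply to the dose?** This is an inference. The calendar calls dosing Day 0 and uses Day 1 for V4. But the heading concerns criteria before treatment, the study gives a single dose (5.3), and 5.2.2 lists no later cycles. The V3 dose is the only sensible reading.

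**Who is affected?** PPS moves in steps of 10, so a patient who meets entry but fails the gate without any decline is one who is at 40% at V0 and still at 40% at V3.

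**Burden that aligned thresholds would avoid.** V0 lasts up to 60 minutes, but it is the visit that establishes eligibility and would take place anyway. For the rest, 5.1.2 states "The duration of V1 will be up to 90 min (30 min assessment + 60 min preparation"), and gives V2 up to 75 minutes. So 90 + 75 = 165 minutes at most. Washouts for the SSRIs and SNRIs in the section 9 table, in days:

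- duloxetine 3, venlafaxine 3, paroxetine 5, sertraline 6, escitalopram 7, citalopram 8
- fluoxetine 45

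**The plan's own intervals.** Clopper-Pearson 90% limits for 6/10 are 30.4% to 85.0% (printed 30.3% to 85.0%), and for 9/15 they are 36.0% to 80.9% (printed 36.0% to 81.0%). These agree to within 0.1 point. They do not involve the PPS thresholds, so nothing here changes them.

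**Effect on the benchmark, if recruited means enrolled.** Completers needed = 0.60 × 15 = 9. Let k be the number of the 15 barred because they stay at 40%. The documents give no k, so a range is shown. Highest attainable rate = (15 − k)/15. Completion needed among the rest = 9/(15 − k).

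| k | Highest attainable rate | Completion needed among the rest |
|---|---|---|
| 0 | 100% | 9/15 = 60.0% |
| 1 | 14/15 = 93.3% | 9/14 = 64.3% |
| 2 | 13/15 = 86.7% | 9/13 = 69.2% |
| 3 | 12/15 = 80.0% | 9/12 = 75.0% |

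Each barred patient costs 1/15 = 6.7 points. With k = 5, ten patients could still be treated if no one else is lost, which is the minimum in 13.3.1. With k = 6 only nine could be.

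**Which denominator?** Recruited is not defined. Enrolled is the better reading: 13.3.1 recruits 15 to allow for some who cannot complete the intervention, and 4.1 provides for registered subjects who never receive therapy. Against it, 13.3.2 says "The Safety Population will consist of all enrolled participants who receive study treatment" and uses that set for participant accountability, and 13.3.1 also speaks of treated patients. The point is not settled.

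**The case against.** A gate at dosing that is stricter than entry can be deliberate, and a patient at 40% might improve to 50%. Both are possible, but the text gives no such rationale. The suicide-risk, delirium and medication items in 5.2.1 re-check entry exclusions. The performance item is the one that re-checks a numerical entry threshold at a higher level.

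Investigators also have discretion. Sections 3.2.8 and 3.2.12 let them exclude a patient judged unsuitable, 5.5 lets them stop therapy, and the PPS is recorded at V0, V1 and V2. An alert team could therefore avoid the problem. That softens the consequence but does not reconcile the two rules.

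The strongest objection concerns direction. A reader might infer that 50% is the true value and that entry must be raised to it. The documents do not show this. Section 3.1.4 names its instrument correctly and 5.2.1 does not, and 5.2.1 also carries cycle headings in a single-dose study, so 50% could be the leftover. The visible list of changes begins at item 8, so a reason given earlier cannot be excluded. This objection stands.

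A reader might also overstate the burden. Adding V0 would give 225 minutes, but V0 occurs under any entry threshold. The 45-day washout is fluoxetine alone; the other listed SSRIs and SNRIs take 3 to 8 days. A 45-day washout would also have to begin before V1, which the calendar places no more than three weeks before dosing.

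**Conclusion.** The protocol is wrong as written on this point and should be corrected. An entry threshold of 40% and a treatment threshold of 50% on a misnamed score are not reconciled anywhere in the text. The conflict rests on reading the 5.2.1 score as the PPS and its heading as the V3 dose. Both are inferences, and both are likely.

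The size per affected patient is up to 165 minutes of preparation visits and assessments plus any taper. If recruited means enrolled, there is also a loss of 6.7 points from the attainable feasibility rate. The number affected is unknown and may be zero.

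A reader might infer that the sample size, the intervals or the benchmark is undermined. The documents do not support that: the target of 15 and the printed intervals stand, and the benchmark effect needs both the denominator reading and at least one patient who stays at 40%. Because reasons for dropout are a listed outcome, any such loss would be visible afterwards, though too late for the patient. Nor is the survival statement in 13.3.1 misapplied, since it is already confined to PPS 50% and above.

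**What to change.** In 5.2.1, name the Palliative Performance Scale (Appendix A3) and use the same threshold there as in 3.1.4. The investigators should confirm which value is current.

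- **50% in both.** This matches the existing dosing gate and the population cited in 13.3.1, which then needs no change. A patient who falls to 40% before V3 is still not dosed, but that is clinical decline, which the recruitment target already allows for. The cost is a narrower entry pool, by a number the documents do not give.
- **40% in both.** This keeps the current entry rule. It is a clinical safety decision and not a wording change: Appendix A3 describes patients at 40% as spending most of their time in bed and possibly drowsy or confused, and the session lasts 8 hours.
- **A stricter dosing gate, if intended.** State it, give the reason, and do not start preparation or taper while a patient is below it.

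The first two options need only a short amendment to 3.1.4 or 5.2.1; the third also needs a sentence on when preparation and taper may start. None needs a new data item, because the PPS is already scheduled at every visit.

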5.2.2. Subsequent Cycles

None

5.3. Agent Administration

Administration – A capsule of psilocybin is administered orally with a full glass of water. Capsules should not be opened or chewed.

Dosing – This is a single dose study. Capsules contain 25 mg of pharmaceutical grade psilocybin, corresponding to the recommended dose in previous studies of healthy volunteers^{64,65} and cancer patients^{8,9,27}.

Observation period – The participant will have adequate counselling and preparation ahead of dosing, and after ingesting the dose will be attended by two therapists, for the subsequent 8 hours. The setting will minimize distraction and interruption, and the patient will be attended following the dose by the therapists trained in providing reassurance and a safe environment until the effects of the single dose have dissipated. Upon discharge from the study setting, the patient will be delivered to the care of a responsible individual who can observe the patient for the remainder of 24 hours after the dose was administered.

Protocol specific procedures –Blood pressure and heart rate will be measured at the following time-points after psilocybin administration (V3): 30, 60, 120, 180, 240, 300, and 360 min (± 10 minutes). Although there have been no reports of their use in well reported clinical trials with oral psilocybin, medications should be available for the treatment of causal symptomatic hypertension, agitation, or severe psychosis. Typically, these supplies are two dosage units of labetalol, nitroglycerin, lorazepam and/or diazepam, and risperidone or similar orally-disintegrating antipsychotic.

Oral Agents – Participants will be advised to avoid consuming high fat meals for one hour before and after study drug consumption. Examples of foods to avoid include those high in butter, cream, oil, cheese, whole milk, mayonnaise, salad dressing, jam, syrup, honey, nuts, as well as

soft drinks, juices, sweets or desserts, pastas, breads, crackers, chips and meats. No other protocol specific procedures are necessary.

Caregiver Precautions – Study participants should not drive or operate heavy machinery for 24 hours post study drug consumption.

5.4. **General Concomitant Medication and Supportive Care Guidelines**

Psilocybin is contraindicated in participants who are on monoamine oxidase inhibitors or who have a known sensitivity to the drug or its metabolites. It is contraindicated in medications that are known uridine diphosphate glucuronosyltransferase enzyme modulators. It is contraindicated in patients with schizophrenia or bipolar disease, or in those with first degree relatives with these disorders. The concurrent use of selective serotonin reuptake inhibitor/serotonin-norepinephrine reuptake inhibitors (SSRI/SNRI) medications is assumed to be contraindicated due to the potential to increase the risk of serotonin syndrome and/or to attenuate the binding of psilocin to the HT2A receptor.

Prior to enrollment participants will be screened per the clinical protocol for contraindicated psychologic conditions or interacting medications by a licensed physician on the study team.

Because there is a potential for interaction of psilocybin with other concomitantly administered drugs through the cytochrome P450 system, the study team will review the concurrent use of all other drugs, over-the-counter medications, or alternative therapies at every visit. The PI should be alerted if the participant is taking any agent known to affect or with the potential to affect selected CYP450 isoenzymes. Appendix C presents guidelines for identifying medications/substances that could potentially interact with the study agent(s).

5.5. Criteria for Taking a Participant Off Protocol Therapy

The planned duration of therapy is a 2 to 4 weeks, including 2 preparation sessions, 1 dosing session with a single intake of the study agent and 2 integration sessions. Treatment will be halted in the setting of:

- Inability to ingest study medication on the dosing day (V3)
- Intercurrent illness that prevents administration of treatment
- Unacceptable adverse event(s)
- Participant demonstrates an inability or unwillingness to comply with the oral medication regimen, the psychotherapy support regimen and/or documentation requirements
- Participant decides to withdraw from the protocol therapy
- General or specific changes in the participant's condition render the participant

unacceptable for treatment in the judgment of the treating investigator

Participants will be removed from the protocol therapy when any of these criteria apply. The reason for removal from protocol therapy, and the date the participant was removed, must be documented in the case report form (CRF). Alternative care options will be discussed with the participant.

When a participant is removed from protocol therapy and/or is off of the study, the participant's status must be updated in OnCore in accordance with REGIST-OP-1.

